Clinical & laboratory investigations	
For Events of Deep Vein Thrombosis (DVT) within 15 days post-op.)
 
All of the patients underwent Routine bilateral compression Doppler.
 
For Clinical PE (Pulmonary Embolism) Events from Day of surgery and During Hospitalization period or end of study
 
Clinical PE events PE (Pulmonary Embolism) events were confirmed by spiral CT.
 
For follow up:
 
APTT should be done before the first dose then after 4 & 8 hours of the first dose, then on days 1,8,15 post operatively.

Study duration	
Enrolment period: 3 months duration
 
Follow-up duration: Follow-up per patient will be for a period of 15 days

Eligibility Criteria	
Inclusion Criteria:
 
 18 years of age or older Body Weight >60 kg Patients undergoing major orthopedic operations

	
Patients ready to sign informed consent form (ICF) Patients should discontinue any agents that affect haemostasis prior to the study medication use unless strictly indicated. These agents include medications such as: anticoagulants, thrombolytics, non-steroidal anti-inflammatory agents (including Ketorolac tromethamine), preparations containing aspirin, systemic salicylates, ticlopidine, dextran 40, clopidogrel, other anti-platelet agents including glycoprotein IIb/IIIa antagonists or systemic glucocorticoids.
 
Exclusion Criteria:
 
Significant bleeding injury such as solid organ laceration or intracranial bleed at discretion of attending physician Hypersensitivity to Hirudin or prior documented Allergy to its components Pregnant or breast feeding Hemorrhagic stroke in preceding 3 months abnormal baseline coagulation characterized by an INR >1.4, obtained at the discretion of the treating clinician Required therapeutic anticoagulation for atrial fibrillation, prior VTE, or mechanical heart valve Patients with a history of coagulation disorder Treatment with concomitant anti-platelet agent other than aspirin 326 mg or more daily (Platelet count < 100 X10⁹ /dl) Active bleeding Subjects with a life expectancy less than 1 month

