6.2. The operative Phase

During this phase, patient's registries for the type of surgery done, Type of anesthesia, patient position and type of prosthesis, & blood transfusion during surgery should be recorded. And IMP dispensing 6 hours after surgery or upon adequate hemostasis will be done. APTT will be done 4 & 8 hours after the first dose

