6.3. The Follow-up Phase

During this phase, which is approximately 15 days, PE which is confirmed by spiral CT chest, any new DVT appears also to be confirmed by Doppler ultrasound, Bleeding assessment, APTT will be done on days 1, 8 & 15, concomitant medications, Hospital stay and any adverse event data will all be recorded

7. FLOW CHARTS:

7.1. STUDY FLOW CHARTS:

Activity	Pre-operative phase (Screening)	Operative phase (Day 0)	Follow-up 1 (Day 1)	Follow-up 2 (Day 8)	Follow-up 3/ End of Study (Day 15)
ICF Signature	×				
Inclusion/Exclusion Criteria	×				
Demographic Data	×				
Medical History	×				
Vital signs	×				
Concomitant Medication	×				
Physical Examination	×				

Laboratory investigation	×		×	×	×
Type of surgery		×			
Assessment of bleeding		×	×	×	
IMP Administration		×	×	×	×
Assessment of DVT			×	×	×
Assessment of PE			×	×	×
Assessment of therapeutic response					×
APTT	×	×	×	×	×
Adverse Event		×	×	×	×
Study completion					×

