7.2. STUDY PHASES

The study consists of 3 phases:

Visit 1: Preoperative phase (screening)

- ❖ Patient Screening (Check eligibility)
- ❖ Signed ICF
- ❖ Gathering Patient Information as Demographic, Vital Signs, BMI, Physical Examination, Medical History, Concomitant medications
- ❖ Laboratory Investigations (Hb, PLt count, APTT, INR, SGPT, SGOT, Serum Albumin, Serum Bilirubin, serum creatinine, Creatinine clearance, Random blood sugar)
- ❖ Patients main complaint (Knee, Hip)

Operative phase (Day 0)

Patient Data to be collected:

- ❖ Type , Date of surgery
- ❖ Type of anaesthesia
- ❖ Patient position
- ❖ Type of prosthesis
- ❖ Blood transfusion

Start of IMP administration.

APTT 4 & 8 hours after IMP administration

Visit 2: Post operative phase (Follow-up 1 (Day 1))

- ❖ Assessment of bleeding
- ❖ Type of blood transfusions
- ❖ Assessment of DVT
- ❖ Routine bilateral compression Doppler (confirmation for DVT)
- ❖ Assessment of PE
- ❖ Spiral CT (confirming PE)
- ❖ IMP administration
- ❖ Laboratory investigations (Hb%, Platelets count)
- ❖ APTT

Assessment will be done in the hospital, as post-operative period before discharge from hospital.

Visit 3: Follow-up 2 (Day 8)

- ❖ Assessment of bleeding
- ❖ Type of blood transfusions
- ❖ Assessment of DVT
- ❖ Routine bilateral compression Doppler (confirmation for DVT)
- ❖ Assessment of PE
- ❖ Spiral CT (confirming PE)
- ❖ IMP administration
- ❖ Laboratory investigations (Hb%, Platelets count)
- ❖ APTT

Assessment in day 8 will be done from outpatient clinic in most patients.

Visit 4: Follow-up 3/ End of Study (Day 15)

- ❖ Assessment of bleeding
- ❖ Type of blood transfusions
- ❖ Assessment of DVT
- ❖ Laboratory Investigations
- ❖ Routine bilateral compression Doppler (confirmation for DVT)
- ❖ Assessment of PE
- ❖ Spiral CT (confirming PE)
- ❖ APTT
- ❖ End of Study

Assessment in day 15 will be done from outpatient clinic.

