8. STUDY OUTCOME MEASURES

8.1. Primary Endpoints

Primary end points included new onset symptomatic thrombosis requiring medical or surgical intervention or death due to thrombosis defined as fatal PE, ischemic

Sponsor: Minapharm Pharmaceuticals
Protocol Number: Sub-Thromb-001
Version: 1 amendment 1

stroke, mesenteric thrombosis, or myocardial infarction.

The number of clinical PE events will be measured by spiral CT

Mean changes in APTT where it will be done before first dose, 4 & 8 hours after first dose then on days 1,8,15 post operatively

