12. TREATMENT OF TRIAL PARTICIPANTS

12.1. Description of Study Medication(s)

Because thrombin plays a central role in thrombogenesis, the goal of most treatment regimens is to block thrombin generation or inhibit its activity.

1- r-Hirudin binds directly with thrombin to its active & fibrinogen binding site.

2- r-hirudin does not require access to heparin binding site & can thus neutralize clot bound thrombin. Hence, down regulating thrombin generation & potentially enhancing early revascularization.

Direct thrombin inhibitors were developed to overcome the inability of the heparin/antithrombin complex to inactivate bound thrombin. In contrast to heparin and low-molecular-weight heparin, which catalyze the inactivation of thrombin and activated factor X (factor Xa) by antithrombin, direct thrombin inhibitors bind to thrombin and block its interaction with its substrates.

II- They do not bind to plasma proteins, direct thrombin inhibitors produce a more predictable anticoagulant response than heparin.

III- Unlike heparin, direct thrombin inhibitors do not interact with platelet factor 4 or high-molecular-weight multimers of von Willebrand factor. Consequently, the activity of direct thrombin inhibitors in the vicinity of a platelet-rich thrombus is not compromised.

IV- Finally, thrombin bound to fibrin or fibrin degradation products is susceptible to inactivation by direct thrombin inhibitors. Because the active site of thrombin is not involved in the interaction of the enzyme with fibrin, it remains accessible to active site-directed thrombin inhibitors. Consequently, these agents inactivate fibrin-bound thrombin without displacing the enzyme from fibrin. In contrast, bivalent thrombin inhibitors, such as Hirudin and bivalirudin, displace bound thrombin during the inhibition reaction by competing with fibrin for access to exosite 1 on thrombin.

Dose of Thrombexx®:

In DVT Prophylaxis: 15 mg twice daily, subcutaneous for 15 days

In case of renal insufficiency, the dose is titrated because r-Hirudin is excreted renally.

According to Creatinine clearance:

Creatinine clearance > 31-60 ml/min (5 mg s.c twice daily)

Creatinine clearance < 31 ml/min (1.7 mg s.c twice daily)

In case of patients who will receive spinal anesthesia; Thrombexx will be given 8-10 hours before puncture/catheter and 2-4 hours after puncture/catheter manipulation or removal, as per European Guidelines.

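### Follow-up APTT (Days 1, 8 and 15) has no stated time after injection and the protocol disagrees on Day 15 dosing, so changes at those visits cannot be separated from sampling time

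*Protocol*

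**What the plan says.** **Sampling times.** Protocol 6.2 fixes the first-dose samples: "APTT will be done 4 & 8 hours after the first dose". Protocol 6.3 gives the later samples by day only: "APTT will be done on days 1, 8 & 15". The synopsis and Protocol 8.1 have the same split, and SAP 2.2, 2.3 and 4.1 repeat it. No section gives an hour after injection, a peak or trough rule, or a window for Days 1, 8 and 15.

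**Dosing and setting.** Protocol 12.1 states: "In DVT Prophylaxis: 15 mg twice daily, subcutaneous for 15 days". Protocol 7.2 places Day 1 in hospital and Day 8 in the outpatient clinic for most patients. For the last visit it says: "Assessment in day 15 will be done from outpatient clinic".

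**Day 15.** In the flow chart (Protocol 7.1) the row "IMP Administration" is marked at Day 0, Day 1, Day 8 and Day 15. In Protocol 7.2, Visits 2 and 3 list both study drug and APTT. The entry headed "Visit 4: Follow-up 3/ End of Study (Day 15") lists APTT but not study drug. The synopsis gives a total of 15 days and also says that treatment runs to the end of the study.

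**Use of the values.** Protocol 8.1 lists under primary endpoints: "Mean changes in APTT where it will be done before first dose, 4 & 8 hours after first dose then on days 1,8,15 post operatively". SAP Table 10 has six columns (before first dose, 4 h, 8 h, Days 1, 8 and 15) with mean and SD, % change and p-values. It names neither the reference for % change nor the test, and has no row for time since the last injection. APTT also feeds a fold-rise limit in the synopsis stopping rules and in Protocol 15.3 and 18.5.1, again without a sampling time.

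**The concern.** With twice-daily injections, the level of a short-acting anticoagulant rises and falls within each dosing interval, and APTT is expected to follow. A Day 8 sample may be taken shortly after an injection or just before the next one, and nothing in the plan says which. Table 10 then compares that value with samples taken at known hours. A change from Day 0 to Day 8 could reflect drug effect, the hour of the clinic visit, or both, and the table gives no means of telling them apart. The normal/abnormal rows have the same problem.

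Day 15 adds a second uncertainty: one part of the protocol has the patient still receiving drug and another does not. An average over patients on and off drug has no single meaning.

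At stake is the interpretation of an endpoint that Protocol 8.1 and SAP 4.1 call primary. If the clock times are not recorded during the study, they may not be recoverable afterwards.

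**Working it through.** The plan gives no numerical figure for APTT, so there is none to reproduce. The check has three parts.

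**1. Does the dosing rule settle Day 15?** Assume injections exactly 12 h apart and none missed. Fifteen days twice daily is 15 × 2 = 30 doses. The 30th falls 29 × 12 = 348 h, or 348/24 = 14.5 days, after the first.
- First dose at 08:00 on Day 0: last dose at 20:00 on Day 14.
- First dose at 18:00 on Day 0: last dose at 06:00 on Day 15.

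The switch is at noon. The first dose depends on the time of surgery and on haemostasis, so the rule allows either. With an assumed 10:00 clinic visit on Day 15, the first patient is sampled 14 h after the last injection and the second 4 h after. The dose count does not resolve the conflict between flow chart and visit list.

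**2. How far can sampling time alone move the value?** The documents give no APTT profile, so the shape is assumed. The APTT ratio to pre-dose rises linearly from trough T to peak P at 2 h. The excess over 1 then declines exponentially back to trough at 12 h:

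R(t) = 1 + (P − 1)·exp(−k(t − 2)), with k = ln[(P − 1)/(T − 1)]/10.

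For a sampling time uniform over 0 to 12 h, the mean is [2(P + T)/2 + 10 + (P − T)/k]/12.

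Worked case, P = 1.6 and T = 1.2: k = ln(0.6/0.2)/10 = 0.1099. R(4) = 1 + 0.6·exp(−0.2197) = 1.48. R(8) = 1 + 0.6·exp(−0.6592) = 1.31. Mean = (2.8 + 10 + 0.4/0.1099)/12 = 1.37.

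| Peak/trough (assumed) | 4 h | 8 h | Random-time mean | Minus 4 h | Minus 8 h | SD from timing |
|---|---|---|---|---|---|---|
| 1.6/1.2 | 1.48 | 1.31 | 1.37 | −0.11 | +0.06 | 0.12 |
| 1.8/1.2 | 1.61 | 1.35 | 1.44 | −0.16 | +0.10 | 0.17 |
| 2.0/1.3 | 1.79 | 1.49 | 1.59 | −0.19 | +0.11 | 0.20 |

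The differences are taken before rounding. The same unchanged drug effect looks like a fall against 4 h and a rise against 8 h. Against pre-dose (ratio 1), the % change at a follow-up visit can lie anywhere from 20 to 60, 20 to 80 or 30 to 100 across the three profiles, depending only on the hour.

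With N = 100 and independent random times, the timing SD adds a standard error of 0.12/√100 = 0.012 to 0.20/√100 = 0.020. The noise in a mean is therefore small; a systematic shift does not shrink with N.

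**3. Could a real change also be present?** The table above gives the first dose the repeated-dose profile, so it cannot show this. A one-compartment model can (all inputs assumed: absorption half-life 0.9 h, elimination half-life 1.5 to 6 h, 20 doses 12 h apart):

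C(t) = ka/(ka − ke)·[exp(−ke·t) − exp(−ka·t)], summed over doses.

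Relative to the first-dose 4 h level, the repeated-dose level is 1.30 to 1.65 at 2 h, 0.03 to 0.57 at 12 h and 0.00 to 0.14 at 24 h after the last dose. At the same hour (4 h) it is 1.01 to 1.36. Genuine accumulation and sampling time can both be in the follow-up values, and untimed samples cannot separate them.

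**The case against.** A reader might infer that Table 10 measures sampling time instead of drug effect. The documents do not support that. Under the assumed profiles the ratio to pre-dose stays at 1.20 or above at every hour of the dosing interval, so drug effect remains visible; it is confounded, not replaced.

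A reader might also infer a spurious decline from the 4 h and 8 h values. Table 10 does not name either as its reference, and it has a pre-dose column that is at least as natural a choice. The sign also depends on the column chosen, as the table above shows. This objection stands: the bias has no fixed direction. It does not remove the problem, because the size of a change from pre-dose still depends on the hour.

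A third inference is that Days 0 to 15 are 16 calendar days and so contradict 15 days of dosing. They need not: the 30th dose can fall on Day 15. The Day 15 conflict rests on the flow chart against the Visit 4 list.

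On practice, Day 1 is in hospital and clinics keep regular hours, so uniform random timing is only an illustration. The CRF was not among the documents and may already record both times. That would preserve the data, but the plan would still lack a rule for using them.

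On weight, APTT is absent from the synopsis endpoints and from the primary analysis variables (Protocol 17.2.1, SAP 8.2.1). That stands and limits the reach of the point.

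**Conclusion.** The point holds in a limited form. Follow-up APTT is untimed relative to injection, and the protocol contradicts itself on Day 15 dosing. The Day 1, 8 and 15 changes in Table 10 therefore cannot be separated from sampling time, and the Day 15 value may be on or off drug.

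The sizes in the table above depend wholly on the assumed peaks, troughs, curve shape and uniform timing. They show that the effect can matter and can take either sign; they do not predict this trial's values.

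It would be wrong to infer that the trial's efficacy result is undermined. The pre-dose, 4 h and 8 h comparisons are timed and stand, and the thrombosis and PE results do not depend on APTT. This should be corrected because the remedy is simple and unrecorded times may be lost. It does not threaten the study's main conclusions.

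**What to change.** - In Protocol 6.3, 7.2 and 8.1 and SAP Table 10, schedule the follow-up endpoint sample at one post-injection time already used on Day 0 (4 h or 8 h).
- As a minimum, record the clock times of the last injection and of the sample, and compare only like-timed values.
- Name the pre-dose value as the Table 10 reference for % change, and name the test behind each p-value.
- Reconcile the flow chart with the Visit 4 list on Day 15 dosing, together with the synopsis wording on 15 days and on treatment to the end of the study. Label the Day 15 APTT as on or off drug accordingly. No view is taken here on which dosing statement is right.
- The APTT limit in the synopsis, 15.3 and 18.5.1 also states no sampling time. The sponsor should reconcile this; no clinical rule is proposed.

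The cost is protocol and SAP wording. In addition, outpatient visits must be timed to the injection or, under the minimum option, two time fields must be captured if the CRF lacks them.

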7.2. STUDY PHASES

The study consists of 3 phases:

Visit 1: Preoperative phase (screening)

- ❖ Patient Screening (Check eligibility)
- ❖ Signed ICF
- ❖ Gathering Patient Information as Demographic, Vital Signs, BMI, Physical Examination, Medical History, Concomitant medications
- ❖ Laboratory Investigations (Hb, PLt count, APTT, INR, SGPT, SGOT, Serum Albumin, Serum Bilirubin, serum creatinine, Creatinine clearance, Random blood sugar)
- ❖ Patients main complaint (Knee, Hip)

Operative phase (Day 0)

Patient Data to be collected:

- ❖ Type , Date of surgery
- ❖ Type of anaesthesia
- ❖ Patient position
- ❖ Type of prosthesis
- ❖ Blood transfusion

Start of IMP administration.

APTT 4 & 8 hours after IMP administration

Visit 2: Post operative phase (Follow-up 1 (Day 1))

- ❖ Assessment of bleeding
- ❖ Type of blood transfusions
- ❖ Assessment of DVT
- ❖ Routine bilateral compression Doppler (confirmation for DVT)
- ❖ Assessment of PE
- ❖ Spiral CT (confirming PE)
- ❖ IMP administration
- ❖ Laboratory investigations (Hb%, Platelets count)
- ❖ APTT

Assessment will be done in the hospital, as post-operative period before discharge from hospital.

Visit 3: Follow-up 2 (Day 8)

- ❖ Assessment of bleeding
- ❖ Type of blood transfusions
- ❖ Assessment of DVT
- ❖ Routine bilateral compression Doppler (confirmation for DVT)
- ❖ Assessment of PE
- ❖ Spiral CT (confirming PE)
- ❖ IMP administration
- ❖ Laboratory investigations (Hb%, Platelets count)
- ❖ APTT

Assessment in day 8 will be done from outpatient clinic in most patients.

Visit 4: Follow-up 3/ End of Study (Day 15)

- ❖ Assessment of bleeding
- ❖ Type of blood transfusions
- ❖ Assessment of DVT
- ❖ Laboratory Investigations
- ❖ Routine bilateral compression Doppler (confirmation for DVT)
- ❖ Assessment of PE
- ❖ Spiral CT (confirming PE)
- ❖ APTT
- ❖ End of Study

Assessment in day 15 will be done from outpatient clinic.

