8.2. Secondary Endpoints

Major Bleeding: was defined as clinically evident hemorrhage associated with a hemoglobin decrease ≥ 2 g/dL that leads to a transfusion of ≥ 2 units of whole blood or packed red cells outside of the perioperative period (time from the start of the surgery or procedure and up to 12 hours after), or hemorrhage that is intracranial, retroperitoneal, or into a prosthetic joint.

Number of any reported (AE) or (SAE) during the study duration.

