9.3 Secondary End Point

Table 11 Proportion of patients experienced major bleeding

		Day 1	Day 8	Day 15	p-value
Assessment of Bleeding:	Normal, N (%)				
	Abnormal, N (%)				
Type Of Blood Transfusions:	Whole Blood, N (%)				
	RBCs, N (%)				
	Platelets, N (%)				
	Plasma, N (%)				

Table 12 *Number and percent of Adverse Event among treatment groups*

	N = 100	p-value
Total No of AE, N (%)		
AE1, N (%)		
AE2, N (%)		
AE3, N (%)		

Table 13 *Number and percent of Serious Adverse Event among treatment groups*

	N = 100	p-value
Total No of SAE, N (%)		
SAE1, N (%)		
SAE2, N (%)		
SAE3, N (%)		

Table 14 *Percent Change in mean Hb%*

	Screening	Day 1	Day 8	Day 15	p-value
Hb%, (mean ± SD)					
% change					
p-value					

Table 15 *Percent Change in mean Platelets count*

	Screening	Day 1	Day 8	Day 15	p-value
Platelets count, (mean ± SD), x 10³/μL					
% change					
p-value					

Table 16 *Percent Change in mean Systolic BP*

	Screening	Day 0	Day 1	Day 8	Day 15	p-value
Systolic BP, (mean ± SD), mmHg						
% change						
p-value						

Table 17 *Percent Change in mean Diastolic BP*

	Screening	Day 0	Day 1	Day 8	Day 15	p-value
Diastolic BP, (mean ± SD), mmHg						
% change						
p-value						

Table 18 *Percent Change in mean Sitting Pulse Rate*

	Screening	Day 0	Day 1	Day 8	Day 15	p-value
Sitting Pulse Rate, (mean ± SD), beats /min						
% change						
p-value						

Table 19 *Percent Change in mean Oral Temperature*

	Screening	Day 0	Day 1	Day 8	Day 15	p-value
Oral Temperature, (mean ± SD), °C						
% change						
p-value						

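### The listed data items and SAP Table 11 name transfusion type only, so they do not support the two-unit, outside-12-hours limb of major bleeding

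*Protocol*

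**What the plan says.** Protocol 8.2, repeated in the synopsis and in SAP 4.2, defines major bleeding by two alternative limbs.

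- **Transfusion limb.** The bleeding must be clinically evident, and the laboratory criterion is a "hemoglobin decrease ≥ 2 g/dL". The patient must also have needed, as a result, blood products in this amount and at this time: "transfusion of ≥ 2 units of whole blood or packed red cells outside of the perioperative period". The excluded period is defined as "time from the start of the surgery or procedure and up to 12 hours after".
- **Critical-site limb.** Alternatively, "hemorrhage that is intracranial, retroperitoneal, or into a prosthetic joint".

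The proportion of patients with major bleeding is a named secondary analysis variable (Protocol 17.2.2, SAP 8.2.2).

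The data items are these:

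- Protocol 6.2 says that "blood transfusion during surgery should be recorded". The operative-phase list in 7.2 has a bare transfusion item and "Type , Date of surgery".
- Visits 2, 3 and 4 in Protocol 7.2 each list a bleeding assessment and "Type of blood transfusions".
- SAP Table 7 has numbered placeholder categories for operative transfusion.
- SAP Table 11 carries the major-bleeding title. Its rows are a Normal/Abnormal bleeding assessment and "Type Of Blood Transfusions", split into whole blood, red cells, platelets and plasma, by visit.

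**The concern.** The transfusion limb depends on a count (at least two units) and a time (outside a window that closes 12 hours after surgery). The visit lists and the table shell ask for neither. They ask which product was given, and that is the one feature of a transfusion that cannot by itself separate a qualifying event from a non-qualifying one.

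The safety objective is framed in terms of serious bleeding, so this proportion is the result that answers it. If sites record what the lists name and no more, a patient given one unit and a patient given several look alike. So do a transfusion at hour 10 and one at hour 14. Whether the patient counts would then be settled by chart review after the fact, with no derivation rule in the SAP to guide it.

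**Working it through.** The documents give no planned or expected figure for major bleeding, so there is no number to reproduce. The sample-size statement in Protocol 17.1 concerns DVT. The check is therefore to match each element of the definition to the items that the plan lists.

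| Element of the definition | Listed item | Enough to decide? |
|---|---|---|
| Clinically evident bleeding | Bleeding assessment at Visits 2-4; Normal/Abnormal in Table 11 | Partly |
| Haemoglobin fall of at least 2 g/dL | Haemoglobin at screening, Day 1 and Day 8 (Protocol 7.2) and Day 15 (SAP Table 14) | Partly: scheduled values only, and Table 14 plans means and percent change |
| Whole blood or packed red cells | Transfusion type | Yes |
| At least two units | None | No |
| Transfusion outside the window | No transfusion date or time; date of surgery only | No, around Day 0 to Day 1 |
| Transfusion given because of the bleed | None | No |
| Intracranial, retroperitoneal or prosthetic-joint site | No site item | Only through adverse event text |

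**Timing.** Protocol 6.2 places the first dose 6 hours after surgery or once haemostasis is adequate, so treatment can begin inside the excluded window. A transfusion reported at the Day 1 visit can lie on either side of the 12-hour cut. Neither end of the interval is on the list, because the transfusion has no time and the surgery has only a date. Transfusions given after Day 1 are past the cut, so for those the missing facts are the units and the link to a bleed.

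**Haemoglobin.** After Day 1 the next scheduled value is Day 8. A fall between those visits that was corrected by transfusion need not appear in the scheduled data. The value just before the transfusion is the one that bears on the definition.

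**Sensitivity of the result.** With N = 100, one patient is 1/100 = 1 percentage point. For x events the exact (Clopper-Pearson) 95% limits are the 0.025 quantile of Beta(x, 100 - x + 1) and the 0.975 quantile of Beta(x + 1, 100 - x). For x = 0 the lower limit is 0 and the upper limit is 1 - 0.025^(1/100) = 3.6%.

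| Events out of 100 | Exact 95% CI |
|---|---|
| 0 | 0 to 3.6% |
| 1 | 0.03 to 5.5% |
| 2 | 0.2 to 7.0% |
| 3 | 0.6 to 8.5% |

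These counts are illustrations and not predictions. They show that reclassifying two patients, from 0 to 2 events, would raise the upper limit from 3.6% to 7.0%.

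**The case against.** The strongest reply is that the plan has other routes to the data. Protocol 16.1 requires every adverse event to be recorded with its onset date, corrective treatment and outcome. Section 16.4.1 requires dated copies of examinations for serious events, and a bleed needing two units would plausibly be serious under 16.4. Sections 11, 13 and 15.2.3 provide for hospital records as source and for monitor verification against them. The CRF is not among the documents, and the lists in 7.2 may be visit headings rather than fields.

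Much of this stands. A reader might infer that the safety endpoint cannot be derived at all, or that the rate would rest on recall. The documents do not support either reading. The critical-site limb needs no units or times, and the adverse event route is a documented record. Nor can it be shown that the CRF lacks the fields. A reader might also infer that haemoglobin stops at Day 8, or that major bleeding is the only safety proportion planned. SAP Table 14 has a Day 15 column, and Tables 12 and 13 report adverse and serious adverse events as N (%).

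The gap itself remains. The adverse event sections do not ask for units or clock time, so they supply them only by chance. The protocol list and the SAP shell, whose rows read like CRF questions, agree on type alone. If the CRF does hold the fields, the remedy is to name them in the plan and add the derivation.

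**Conclusion.** The concern holds for the transfusion limb. As listed, the items in Protocol 7.2 and the SAP Table 11 shell do not give the number of units or the timing that this limb requires, and Table 11 has no row that applies the definition. The critical-site limb can be met without units or times, but it depends on adverse event text because no site item is listed.

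The size of the error cannot be stated as a bleeding rate, because the documents give no transfusion rate. What can be said is that each misclassified patient is worth one percentage point at N = 100, where exact intervals for a handful of events are only a few points wide. This rests on the lists and shells being a fair guide to what is collected.

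This is a secondary endpoint in a descriptive single-arm study with no safety threshold, and a partial route to the data exists. I would rate it as something that should be fixed, ideally before data collection, since later recovery means chart review.

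**What to change.** In Protocol 7.2 (operative phase and Visits 2 to 4):

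- Record the start and end time of surgery. Without clock times the 12-hour window cannot be computed, even if transfusions are timed.
- For each transfusion, record the product, the number of units, the date and time, the last haemoglobin before it, and whether it was given for clinically evident bleeding.
- Record the site of any bleed. A flag built from transfusion fields alone would drop critical-site bleeds that did not also meet the transfusion limb.

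In the SAP, define a patient-level major-bleeding flag that applies both limbs, and report its proportion with a 95% CI as a row in Table 11.

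While editing, reconcile the flow chart in Protocol 7.1, which marks no bleeding assessment at Day 15, with the Visit 4 list in 7.2, which includes one.

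The cost is a few extra CRF fields copied from existing hospital records, plus a short derivation in the SAP. No new test or visit is needed.
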